## **4. SUBJECT DISPOSITION**

### **4.1. Subject Enrollment and Disposition**

#### **4.1.1. Subject Enrollment**

The number and percentage of subjects enrolled in each country and by each investigator within a country will be summarized for all subjects in the Safety Analysis Set by Parts 1 and 2.

The enrollment related data will be listed.

#### **4.1.2. Disposition of Subjects**

A summary of subject disposition will be provided overall and by Parts 1 and 2. This summary will present the number and/or percentage of subjects screened, screen failure subjects who were not enrollment, subjects who met all eligibility criteria and were not enrolled, subjects enrolled, subjects enrolled but not treated, subjects in the Safety Analysis Set, subjects in the FAS.

In addition, the number and percentage of subjects meeting the following criteria will be summarized:

- Prematurely discontinued study drug (with summary of reasons for discontinuing treatment)
- Prematurely discontinued from the study (with summary of reasons for discontinuing the study).

The denominator for the percentage of subjects in each category will be the number of subjects in the Safety Analysis Set.

A data listing of reasons for premature study drug discontinuation will be provided.

### **4.2. Extent of Study Drug Exposure and Adherence**

Extent of exposure to study drug will be examined by assessing the total duration of exposure to study drug and the level of adherence to the study drug specified in the protocol.

#### **4.2.1. Duration of Exposure to Study Drug**

Duration of exposure to study drug will be defined as (last dose date – first dose date + 1), regardless of temporary interruptions in study drug administration, and will be expressed in weeks (recorded to 1 decimal place, eg, 4.5 weeks).

Duration of exposure to study drug will be summarized overall and by Parts 1 and 2 using descriptive statistics (n, mean, SD, median, Q1, Q3, minimum, and maximum). The number and percentage of subjects in the following categories will also be summarized:  $\geq 4$  weeks [28 days],  $\geq 8$  weeks [56 days],  $\geq 12$  weeks [84 days],  $\geq 16$  weeks [112 days],  $\geq 24$  weeks [168 days],  $\geq 36$  weeks [252 days], and  $\geq 48$  weeks [336 days]. These categories start with a cumulative count thus subjects who complete the study will be counted from the first category up.

Time to premature discontinuation of study drug will be analyzed using the Kaplan-Meier (KM) method for all subjects in the Safety Analysis Set and by Parts 1 and 2.

A KM plot of the estimates for time to premature discontinuation will be generated.

#### 4.2.2. Adherence to Study Drug

Study drug regimen adherence will be computed based on pill counts. The numbers of pills of study drug (E/C/F/TAF) dispensed and returned are captured on Study Drug Accountability eCRF.

Adherence (%) of study drug regimen for each study drug will be calculated as follows:

$$\begin{aligned} \text{Adherence (\%)} &= 100 \times \frac{\text{Total Number of Pills Taken}}{\text{Total Number of Pills Prescribed}} \\ &= 100 \times \frac{\sum \text{No. of pills taken at each dispensing period}^{[1]}}{\sum \text{No. of pills prescribed at each dispensing period}^{[2]}} \end{aligned}$$

[1] Number of pills taken at a distinct dispensing period for a study drug is calculated as the minimum of (a) the daily number of pills prescribed for the study drug multiplied by **the duration of treatment** at the dispensing period of the same dispensing date, and (b) the number of pills taken for the study drug (number of pills dispensed minus the number of pills returned). Total number of pills taken is determined by summing the number of pills taken for each study drug contained in the study drug regimen from all evaluable dispensing periods.

[2] Number of pills prescribed at a distinct dispensing period for a study drug is calculated as the daily number of pills prescribed for the study drug multiplied by the **duration of treatment** at the dispensing period of the same dispensing date. Total number of pills prescribed is determined by summing the number of pills prescribed for the study drug from all evaluable dispensing periods.

**The duration of treatment** at a dispensing period for a study drug is calculated as the minimum of (a) the last returned date of the same dispensing period for the study drug, (b) date of premature discontinuation of the study drug, and (c) **next pill dispensing date** of the study drug, minus dispensing date of the study drug.

**The next pill dispensing date** is the following dispensing date of the study drug regardless of the bottle return date.

For a record where the number of pills returned was missing (with “Yes” answered for “Was the Bottle returned?” question), it is assumed the number of pills returned was zero. If the number of pills dispensed was missing or any study drug bottle was not returned or the bottle return status was unknown for the same dispensing date, all records for the same dispensing date for that study drug will be excluded from both denominator and numerator calculation.

Descriptive statistics for adherence to study drug regimen (n, mean, SD, median, Q1, Q3, minimum and maximum) along with the number and percentage of subjects belonging to adherence categories (eg, < 80%, ≥ 80% to < 90%, ≥ 90% to < 95%, ≥ 95%) will be provided overall and by Parts 1 and 2 for subjects who return at least 1 bottle and have calculable adherence during the study in the Safety Analysis Set.

#### **4.3. Protocol Deviations**

A listing will be provided for all enrolled subjects who violated at least one inclusion or exclusion criterion. The listing will include the criteria not met.

## 5. BASELINE DATA

### 5.1. Demographics

Subject demographic data (age, sex, race, and ethnicity) and baseline characteristics (body weight, height, body mass index [BMI]) will be summarized overall and by Parts 1 and 2 using descriptive statistics (n, mean, SD, median, Q1, Q3, minimum and maximum) for continuous data and by the number and percent of subjects for categorical data. The summaries of demographic data and baseline characteristics will be provided using the Safety Analysis Set. Age is calculated as age in years at first dose of study drug.

### 5.2. Baseline Disease Characteristics

The following baseline disease characteristics will be summarized overall and by Parts 1 and 2:

- HIV-1 RNA categories (copies/mL): (a) < 50, (b) ≥ 50
- CD4+ cell count (/μL)
- CD4+ cell count categories (/μL): (a) < 50, (b) ≥ 50 to < 200, (c) ≥ 200 to < 350, (d) ≥ 350 to < 500, and (e) ≥ 500
- CD4 percentage (%)
- HIV risk factors (mode of infection): (a) Heterosexual Sex; (b) Homosexual Sex; (c) IV Drug Use; (d) Transfusion; (e) Vertical Transmission; (f) Other; (g) Unknown
- HIV disease status: (a) Asymptomatic; (b) Symptomatic HIV Infection; (c) AIDS; (d) Unknown
- HBV Surface Antigen Status (Yes, No)
- HCV Antibody Status (Yes, No)
- Estimated GFR by CG (see Section 7.3.2.1)
- Estimated GFR by CKD-EPI (see Section 7.3.2.2)
- Proteinuria by urinalysis (dipstick)
- Tobacco smoking history (Current/Former)
- Genetic mother/father/ brother/sister with myocardial infarction/stroke before 50 years-old?
- Currently using indinavir, lopinavir, or abacavir

- Baseline alanine aminotransferase (ALT) (U/L)
- Baseline aspartate aminotransferase (AST) (U/L)
- Baseline platelet count ( $10^3/\mu\text{L}$ )

A by-subject listing of baseline characteristics will be provided by subject ID number in ascending order.

### **5.3. Medical History**

General medical history data will be collected at screening and listed only. General medical history data will not be coded.

## 6. EFFICACY ANALYSES

### 6.1. Primary Efficacy Endpoint

#### 6.1.1. Definition of Primary Efficacy Endpoint

The primary efficacy endpoint is the proportion of subjects with HIV-1 RNA < 50 copies/mL at Week 12 as defined by PVR.

##### 6.1.1.1. Definition of Pure Virologic Response at Week 12

The following criterion is considered for classifying subjects as a pure virologic responder at Week 12:

- No confirmed rebound (ie, no instances of either HIV-1 RNA  $\geq$  50 copies/mL on 2 consecutive visits or last available HIV-1 RNA  $\geq$  50 copies/mL followed by premature discontinuation of study) by the upper limit of the Week 12 analysis window.

**Note:** For confirmation of virologic rebound, the first HIV-1 RNA datum must occur on or before the upper limit of the Week 12 analysis window. The confirming event (ie, the second of the 2 consecutive HIV-1 RNA values or premature study discontinuation) can occur after the upper limit of the Week 12 analysis window.

Subjects who meet the above criterion are PVRs at Week 12; otherwise subjects are pure virologic failures (PVFs) at Week 12.

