6.3. Treatment Assessments

6.3.1. Treatment Visits (Weeks 4 – 48)

The following evaluations are to be completed at the end of Weeks 4, 8, 12, 16, 24, 36 and 48 unless otherwise specified.

All study visits are to be scheduled relative to the Day 1 visit date. Study visits are to be completed within ± 2 days of the protocol-specified visit date through Week 16 and completed within ± 6 days of the protocol-specified visit date through Week 36, unless otherwise specified. The visit window at Week 48 will be ± 6 weeks of the protocol-specified visit date, which coincides with the Week 48 statistical analysis window for HIV-1 RNA. For the purposes of scheduling the Week 48 visit, a ± 6 day window of the protocol-specified visit date should be used.

Regularly scheduled evaluations will be made on all subjects whether or not they continue to receive study drug.

Note: At the Week 16 visit, the only assessments to be completed are:

- Review of AEs and changes in concomitant medications
- Blood sample collection for the following laboratory analyses:
 - Plasma HIV-1 RNA
 - Plasma sample storage for safety and virology testing
- Document study drug dispensation and accountability for all study drug dispensed.
- Questionnaire: Subject is to read questionnaire by her/himself and write/mark answers directly onto questionnaire.
 - Visual Analog Scale (VAS)

For all other visits, please complete the following:

- Review of AEs and changes in concomitant medications
- Complete physical examination (**Weeks 24 and 48**) (urogenital/anorectal exams will be performed at the discretion of the Investigator)
- Symptom-directed physical examination as needed (**Weeks 4, 8, 12 and 36**)
- 12-lead ECG performed supine (**Week 48 only**)
- Vital signs (blood pressure, pulse, respiration rate, and temperature), including weight
- Urine collection for the following laboratory procedures:
 - Urinalysis and urine chemistry
 - Urine pregnancy test (females of childbearing potential only); positive urine pregnancy tests will be confirmed with a serum test. If the test is positive, the subject will be discontinued.
 - Urine sample storage for possible additional clinical testing
- Blood sample collection for the following laboratory analyses:

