6.4. Post-treatment Assessments

6.4.1. Early Study Drug Discontinuation (ESDD) Visit

If a subject discontinues study drug prior to the Week 48 visit, the subject will be asked to return to the clinic within 72 hours of stopping study drug for the ESDD visit. The subject will be asked to continue attending the scheduled study visits through Week 48.

At the ESDD Visit, any evaluations showing abnormal results indicating that there is a possible or probable causal relationship with the study drug, will be repeated weekly (or as often as deemed prudent by the Investigator) until the abnormality is resolved, returns to baseline, or is otherwise explained.

The following evaluations are to be completed at the Early Study Drug Discontinuation Visit:

- Review of AEs and changes in concomitant medications
- Complete physical examination (urogenital/anorectal exams will be performed at the discretion of the Investigator)
- 12-lead ECG performed supine
- Vital signs (blood pressure, pulse, respiration rate, and temperature), including weight
- Urine collection for the following laboratory procedures:
 - Urinalysis and urine chemistry
 - Urine pregnancy test (females of childbearing potential only); positive urine pregnancy tests will be confirmed with a serum test.
 - Urine sample storage for possible additional clinical testing
- Blood sample collection for the following laboratory analyses:
 - Chemistry profile: alkaline phosphatase, AST, ALT, total bilirubin, direct and indirect bilirubin, total protein, albumin, bicarbonate, BUN, calcium, chloride, creatinine, glucose, potassium and sodium
 - Estimated GFR, according to the Cockcroft-Gault formula for creatinine clearance
 - Hematology profile: CBC with differential and platelet count
 - Plasma HIV-1 RNA
 - CD4+ cell count
 - Plasma sample storage for safety and virology testing
 - **CCI**

- Questionnaire: Subject is to read questionnaire by her/himself and write/mark answers directly onto questionnaire.
 - Visual Analog Scale (VAS)
 - HIV-TSQc
- HIV-1 genotype/phenotype resistance testing for subjects with unconfirmed virologic rebound with HIV-1 RNA value ≥ 50 copies/mL
- Questionnaire: Subject is to read questionnaire by her/himself and write/mark answers directly onto questionnaire.
 - HIV Treatment Satisfaction Questionnaire Change (HIV-TSQc)
- Study drug accountability

6.4.2. 30-Day Follow-up Visit

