8.4. Efficacy Analysis

8.4.1. Primary Analysis

The primary endpoint of pure virologic response (PVR) with HIV-1 RNA < 50 copies/mL at Week 12 will be computed.

The following criteria are considered for classifying subjects as a pure virologic responder at Week 12:

- Subject remains on study treatment
- No confirmed rebound as defined by:
 - HIV-1 RNA \geq 50 copies/mL on 2 consecutive visits;
 - HIV RNA \geq 50 copies/mL during study followed by premature discontinuation of study

Note: For confirmation of viral rebound, the first HIV-1 RNA must occur on or before the upper limit of the Week 12 analysis window, the confirming event (i.e., the second of the consecutive HIV-1 RNAs or premature study discontinuation) can occur after the upper limit of the Week 12 analysis window.

Subjects who meet the above criteria are pure virologic responders at Week 12; otherwise subjects are pure virologic failures (PVF) at Week 12. The 95% CI will be computed using normal approximation to the binomial proportions of PVR

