##### **3.1.2. Full Analysis Set**

The Full Analysis Set (FAS) will include all the subjects who were enrolled and received at least one dose of study drug. For the FAS, all efficacy data will be included, unless specified otherwise. The FAS is the primary analysis set for the efficacy analyses.

Subjects meeting the following criteria will be excluded from the FAS:

- Subjects who took Stribild or Descovy as part of the baseline antiretroviral (ARV) regimen and thus violated the inclusion criterion.

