##### 6.1.1.2. Joint Distribution of Pure Virologic Failure and Study Drug Discontinuation

PVF at Week 48 is defined similarly as PVF at Week 12, except that the time point is at Week 48. For subjects with PVF at Week 48, event time is defined as the day of the first occurrence of confirmed HIV-1 RNA  $\geq$  50 copies/mL or the collection time of last available HIV-1 RNA  $\geq$  50 copies/mL followed by premature discontinuation of study.

Drug discontinuation (DC) is defined as subjects who prematurely discontinued study drug on or prior to the upper limit of the Week 48 analysis window. The premature study drug discontinuation date is the last dose date defined in Section 3.7.1.

To better understand the relationship between study drug discontinuation and pure virologic failure by Week 48, subjects will be classified into the following 4 categories:

- **Success** is defined as subjects who were pure virologic responders and did not discontinue study drug prematurely.
- **PVF alone** is defined as subjects who were pure virologic failures but did not discontinue study drug prematurely.

- **DC alone** is defined as subjects who were pure virologic responders but discontinued study drug prematurely.
- **PVF and DC** is defined as subjects who were pure virologic failures and discontinued study drug prematurely.

For ‘DC alone’ and ‘PVF and DC’ categories, reasons for DC will be grouped into 3 mutually exclusively categories: (1) **DC due to drug**, including discontinuation due to lack of efficacy, death, or AE; (2) **DC due to choice**, including discontinuation due to noncompliance, withdrew consent, protocol violation, or investigator’s discretion (3) **DC due to administration**, including lost to follow-up or pregnancy. For each premature study drug discontinuation group under ‘PVF and DC’ category, outcomes will further be broken down into 3 mutually exclusively categories based on the sequence when PVF and DC occurred: (1) **PVF-DC** is defined as subjects who met the criteria for PVF followed by DC; (2) **PVF/DC** is defined as subjects who met the criteria for PVF and DC at the same time; (3) **DC-PVF** is defined as subjects who had DC first and then met the criteria for PVF.

The pure virologic response analysis will be descriptive in nature using the FAS only. No inferential statistics will be provided.

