### 6.3. Changes From Protocol-Specified Efficacy Analyses

For the primary efficacy endpoint, PVR at Week 12, the protocol specifies that 95% CIs will be generated using the normal approximation method, but in the SAP, both the normal approximation and the exact methods are specified.

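### The SAP drops the protocol's on-treatment condition from the primary Week 12 pure virologic response and does not declare the change

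*SAP*

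**What the plan says.** **Protocol.** Section 8.4.1 and the Statistical Methods part of the synopsis set two conditions for a Week 12 responder. The first is "Subject remains on study treatment"; the second is no confirmed rebound. Anyone who misses either is a pure virologic failure. Section 8.4.2 carries a similar definition to Weeks 24 and 48.

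**SAP.** Section 6.1.1.1 states "The following criterion is considered for classifying subjects as a pure virologic responder at Week 12", in the singular, and lists only the absence of confirmed rebound. Section 6.1.1.2 then sets up a category, *DC alone*, which "is defined as subjects who were pure virologic responders but discontinued study drug prematurely". That group cannot exist under the protocol rule applied at the same time point, so the omission is not a slip of wording.

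**Declared changes.** SAP 6.3 has one entry: "For the primary efficacy endpoint, PVR at Week 12, the protocol specifies that 95% CIs will be generated using the normal approximation method", to which the SAP adds the exact method. The revision table in SAP 11 does not mention the response definition.

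**Data that enter the endpoint.** Protocol 6.3.1 says "Regularly scheduled evaluations will be made on all subjects whether or not they continue to receive study drug". For a patient who stops early, Protocol 6.4.1 adds "The subject will be asked to continue attending the scheduled study visits through Week 48". SAP 3.1.2 says "For the FAS, all efficacy data will be included, unless specified otherwise", and SAP 6.1.1.1 sets no on-treatment limit.

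**The concern.** The two governing documents classify the same patient in opposite ways on the primary endpoint. A patient who stops study drug in week 6, moves to another regimen and stays suppressed is a failure in the protocol and a success for E/C/F/TAF in the SAP. So is a patient who stops with a suppressed value and is never seen again. A patient still on drug with missing data passes under both rules and is not at issue.

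The study is open-label and single-arm, and its main result is one proportion with its interval. A reader of SAP 6.3 would conclude that the endpoint is unchanged apart from the interval method. SAP 1.3 also uses a 100% Part 1 response to assume 95% or higher overall and to reduce the sample to 64, without saying which definition gave that figure.

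A smaller change in the same sentence is also undeclared. The protocol's second rebound arm refers to a value of at least 50 copies/mL at any point in the study before the patient leaves it; the SAP refers to the last value before leaving. Because the protocol treats leaving the study as the confirming event, this is best read as a clarification.

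**Working it through.** **Inputs.** Revised sample 64, assumed rate 95% and stated half-width 5.3 points (SAP 1.3). Original planning: 100 patients, 90%, half-width 5.9 points (Protocol 8.6). Intervals are two-sided 95%, normal and exact (SAP 6.1.3). The Week 12 HIV-1 RNA window ends on Day 98 (SAP Table 3-1). The number *d* off drug by Week 12 without rebound is not given, so it is assumed.

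**Step 1: the plan's own figures reproduce.** Normal half-width = 1.96 × √(p(1 − p)/n).

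- 1.96 × √(0.90 × 0.10/100) = 5.9 points, as stated.
- 1.96 × √(0.95 × 0.05/64) = 5.3 points, as stated.

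**Step 2: direction.** Read the second rebound arm the same way in both documents and take the same patients. Protocol failure is off drug OR rebound. SAP failure is rebound. Every SAP failure is a protocol failure, and the only patients who differ are off drug without rebound. The SAP rate is therefore equal or higher, by 1/64 = 1.6 points per such patient. The two full analysis set definitions also differ (Protocol 8.2.1.1.1, SAP 3.1.2). That is a separate matter and could move the reported rate either way.

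**Step 3: size.** With no rebound and n = 64, the SAP rate is 64/64 = 100% for every *d*, exact 95% CI 94.4 to 100.0. The protocol rate is (64 − d)/64 with Clopper-Pearson limits:

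| d | Protocol rate | Exact 95% CI | Normal half-width |
|---|---|---|---|
| 1 | 98.4% | 91.6–100.0 | 3.0 |
| 2 | 96.9% | 89.2–99.6 | 4.3 |
| 3 | 95.3% | 86.9–99.0 | 5.2 |
| 4 | 93.8% | 84.8–98.3 | 5.9 |
| 5 | 92.2% | 82.7–97.4 | 6.6 |

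If 60 patients are in the full analysis set, 1, 3 or 5 stoppers give 98.3%, 95.0% or 91.7%.

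**Step 4: against the planning figures.** At three stoppers the protocol rate still meets the 95% in SAP 1.3. At four it does not, and the half-width is 5.9 points against the stated 5.3. The 80% level that the synopsis calls unacceptable stays below the exact lower limit at all these counts.

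**Step 5: which counts are plausible.** In the switch study cited in Protocol 1.2.3, 0.9% of patients switched to this drug stopped for adverse events: 0.009 × 64 = 0.6 patients. That figure comes from a report of Week 48 results and leaves out other reasons for stopping.

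**Step 6: do other planned outputs give the protocol rate?**

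- The joint table in SAP 6.1.1.2 ("To better understand the relationship between study drug discontinuation and pure virologic failure by Week 48") covers Week 48 only.
- The exposure summary and Kaplan-Meier curve of drug discontinuation (SAP 4.2.1) describe stopping, not response. The curve uses the Safety Analysis Set.
- The Week 12 snapshot (SAP 6.2.2.3) uses on-treatment data but classifies by the last value in the window, not by confirmed rebound.
- Missing = Failure (SAP 6.2.2.5) fails only missing values, so a suppressed value taken off drug still passes.
- The listing in SAP 6.2.2.2 would let a reader rebuild the count by hand, but it gives no rate and no interval.

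**The case against.** The strongest reply is that a purely virologic endpoint should depend on virology alone. Protocol 6.8 defines virologic failure as rebound, with no reference to stopping drug. That makes the SAP rule defensible as a choice. But 6.8 governs patient management, while 8.4.1 defines the endpoint and says otherwise; the change still has to be declared.

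The second reply is that other outputs nearly fill the gap. SAP 4.2.1 counts patients with at least 84 days of exposure. SAP 6.1.4.1 plans a response analysis that adds back the patients excluded from the full analysis set, so response and exposure will be available on the same patients. The *Success* count in SAP 6.1.1.2 is in substance the protocol definition at Week 48. All of this is true, and it means stopping will not be hidden. None of it is the protocol-defined Week 12 rate with its interval.

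The third reply is that the effect is small. The cited switch study had 97% snapshot success at Week 48, so non-success of every kind was about 3%, or 1.9 of 64. Only the renal impairment study's 92% (8%, or 5.1 of 64) reaches the four- and five-stopper rows, and that is over 48 weeks. If the 100% Part 1 rate came from the protocol rule, Part 1 had no stoppers by Week 12, and any difference would lie in Part 2. Four stoppers breach a planning assumption, not a success criterion, and there is no hypothesis test. These points stand and support a small or zero effect. They do not remove the conflict between the documents.

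**Conclusion.** The point holds and must be fixed. The primary endpoint has two different definitions, the SAP's version can only be equally or more favourable for the same patients, and the change is not declared. Its size is 1.6 points for each of 64 patients who is off drug by Week 12 without rebound. That count is unknown and may be zero; the drug-stopping figure in the protocol suggests a small one. The rates above assume no rebound and illustrative counts. The case for acting rests on the undeclared change to the primary endpoint, not on a demonstrated shift in the result. The sample size arithmetic is correct as stated.

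**What to change.** 1. Report response at Weeks 12, 24 and 48 under the protocol definition beside the SAP definition, each with its 95% CI.
2. State the day through which a patient must remain on drug. The protocol gives none. Day 98, the end of the Week 12 window, is the natural reading because the rebound criterion already uses it; Day 84 is possible and would reclassify a patient who stops between the two.
3. Either keep the protocol definition as primary with the SAP version as a labelled sensitivity analysis, or declare and justify the change in SAP 6.3.
4. List the rewording of the second rebound arm in SAP 6.3 as a clarification. The literal protocol wording need not be restored.
5. State in SAP 1.3 which definition gave the 100% Part 1 rate.

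The cost is SAP wording, one derived flag and one table, all from data already collected. The protocol-defined rate may be slightly less favourable, or identical if nobody stopped drug by Week 12.
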